Comparison of Hearing Aid Fitting Outcomes Between Self-fit and Professional Fit for MDHearing Smart Hearing Aids

NCT05165121

Initial date: 2/28/2020

Final date: 7/13/2020

Exhibit B

MDHearing App Clinical Research Protocol

- Part One: Human Factors Testing To be completed prior to the clinical trials.
 - Subjects
 - o 20 subjects with mild to moderate sensorineual hearing loss.
 - Subjects must have and be able to use a smartphone that is compatible with the MDHearing app.
 - Subjects will not be allowed to participate if they have any signs of middle or outer ear infection or abnormality.
 - All subjects will undergo a hearing evaluation to ensure they do not have any of the following conditions:
 - Visible congenital or traumatic deformity of the ear.
 - History of active drainage from the ear in the previous 90 days.
 - History of sudden or rapidly progressive hearing loss within the previous 90 days.
 - Acute or chronic dizziness.
 - Unilateral hearing loss of sudden or recent onset within the previous 90 days.
 - Audiometric air-bone gap equal to or greater than 15 decibels at 500 Hz, 1,000 Hz, and 2,000 Hz.
 - Visible evidence of significant cerumen accumulation or a foreign body in the ear canal.
 - Pain or discomfort in the ear.
 - Subjects will be at least 18 years old. There are no other limits on subject age.
 - Protocol
 - Subjects will unbox the CORE hearing aid and perform usability tasks in simulated use environments.
 - Subjects will have access to the manuals and quick start guide for the CORE hearing aid and for the MDHearing app.
 - Tasks for usability will include the following:
 - Downloading the MDHearing app.
 - Registering for the MDHearing app.
 - Placing a battery in the CORE hearing aid.
 - Pairing the MDHearing app to the CORE hearing aid.
 - Using the app to take the personalization profile.
 - Using the app to adjust the volume, program, noise reduction, microphone direction, bass, treble, and mid pitched settings.
 - Turning off the CORE hearing aid.
 - Tasks for safety will include the following:
 - Identify how a user knows they are a candidate for a hearing aid. See Identification Information.

- Sound awareness safety. Identification of sounds that should require wearing hearing protection ie mowing the lawn, attending a loud concert, shooting a gun, etc. Recognition that hearing aids do not provide hearing protection.
- Program safety. Recognition that certain programs are not appropriate for certain situations. E.g. Program 4 is a directional microphone program and thus is not appropriate for driving a car due to compromised awareness of sound behind you such as sirens.

Part Two: Clinical Testing Protocol: Laboratory Evaluation of Validity of MDHearing Self-Fitting Method

- Subjects:
 - 75 subjects with mild to moderate sensorineural hearing loss.
 - Subjects will not be allowed to participate if they have any signs of middle or outer ear infection or abnormality.
 - All subjects will undergo a hearing evaluation to ensure they do not have any of the following conditions:
 - Visible congenital or traumatic deformity of the ear.
 - History of active drainage from the ear in the previous 90 days.
 - History of sudden or rapidly progressive hearing loss within the previous 90 days.
 - Acute or chronic dizziness.
 - Unilateral hearing loss of sudden or recent onset within the previous 90 days.
 - Audiometric air-bone gap equal to or greater than 15 decibels at 500 Hz, 1,000 Hz, and 2,000 Hz.
 - Visible evidence of significant cerumen accumulation or a foreign body in the ear canal.
 - Pain or discomfort in the ear.
 - At least one air conduction threshold must be above 25dB. All air conduction thresholds must be below 60db.
 - Subjects will be at least 18 years old. There are no other limits on subject age.
- Protocol and ANSI specs
 - Subjects take the personalization profile on an iPad tablet.
 - Subjects then listen to the same recorded speech passage at their Most Comfortable Listening level 3 times and adjust the aids for comfort (volume, bass, treble, and mid) while the passage is playing. Subjects do not have to make changes if they are content with the sound quality.
 - After each passage, Real Ear measurements will be taken. Gain results at 500, 1000, 2000, and 4000Hz for a 60dB input will be recorded.

• The differences between gain for each frequency will be evaluated per subject. See table below for example:

Subject		500Hz	1000Hz	2000Hz	4000Hz	Total gain
1						deviation
	Passage 1	15dB	18dB	20dB	23dB	
	Passage 2	17dB	19dB	22dB	22dB	
	Passage 3	14dB	18dB	19dB	24dB	
	Average	2.5	1	2.5	1.5	1.9dB
	deviations					

Part Three: Comparative Clinical_Testing Protocol: Clinical Validation of MDHearing Self-Fitting Method

- Subjects
 - 75 subjects with mild to moderate sensorineual hearing loss.
 - Subjects must have and be able to use a smartphone that is compatible with the MDHearing app.
 - Subjects will not be allowed to participate if they have any signs of middle or outer ear infection or abnormality.
 - All subjects will undergo a hearing evaluation to ensure they do not have any of the following conditions:
 - Visible congenital or traumatic deformity of the ear.
 - History of active drainage from the ear in the previous 90 days.
 - History of sudden or rapidly progressive hearing loss within the previous 90 days.
 - Acute or chronic dizziness.
 - Unilateral hearing loss of sudden or recent onset within the previous 90 days.
 - Audiometric air-bone gap equal to or greater than 15 decibels at 500 Hz, 1,000 Hz, and 2,000 Hz.
 - Visible evidence of significant cerumen accumulation or a foreign body in the ear canal.
 - Pain or discomfort in the ear.
 - At least one air conduction threshold must be greater than 25dB. All air conduction thresholds must be less than 60db.
 - Subjects will be at least 18 years old. There are no other limits on subject age.
- First visit
 - A hearing test is performed on all subjects.
 - Subjects complete the Abbreviated Profile of Hearing Aid Benefit (APHAB) and Speech, Spatial, and Qualities of Hearing Scale (SSQ-12).
 - Subjects complete the Quick SIN. (Speech in Noise test)

- All subjects use the MDHearing CORE with the tubing and ComfortTIP that is appropriate for their hearing loss. The tubing and ComfortTIP selection is audiologist fit to half the participants. The other half of the participants chose their own tubing and ComfortTIP. The tubing options are thin tubing with open ComfortTIP or thin tubing with closed ComfortTIP.
- The subjects are split into two groups.
 - The groups are controlled for demographic such as age, gender, length of hearing loss, previous hearing aid use, length of hearing aid use, comfort with technology and level of sensorineural hearing loss.
- Half of the subjects take the MDHearing personalization profile and are fit using NAL NL
 2 fitting software embedded in the MDHearing app. (Self-fit group)
- Half of the subjects are fit using hearing aid fitting software with the NAL NL 2 fitting method. (Audiologist fit group)
- The subjects that are self-fit have access to changing their volume control, programs, bass, treble, and mid pitched settings, noise reduction, and microphone direction using the MDHearing app.
- The subjects that are audiologist fit have access to changing their volume control and programs on the CORE hearing aid. The audiologists have access to changing the bass, treble, and mid pitched settings, noise reduction, and microphone direction using the fitting software.
- Wearing period
 - Subjects wear the hearing aids for one month to acclimate. Minimum of 8 hours per day usage is required.
 - Subjects in the audiology fit group will have one audiology appointment approximately
 2 weeks after being fit. This will give them a chance to have questions answered and for
 fine tuning adjustments to programming as needed.
 - Both groups have access to online rehabilitation programs such as Angelsound, if they wish to use it.
- Second visit One month later
 - Subjects in the self-fit group answer the MDHearing questionnaire.
 - Perform Quick SIN on subjects in both groups. Compare results for statistically significant differences.
 - Ask subjects to complete the Abbreviated Profile of Hearing Aid Benefit (APHAB) and Speech, Spatial, and Qualities of Hearing Scale (SSQ-12). Compare results for statistically significant differences.
 - Perform Real Ear on all subjects using their preferred settings.
 - Compare overall gain settings in relation to hearing loss in both groups. Compare gain settings at 500, 1000, 2000, and 4000Hz as a 4 frequency average in both groups.
 - See Figure 7 in the Bose DeNovo for information on this.

Comparison of Hearing Aid Fitting Outcomes Between Self-fit and Professional Fit for MDHearing Smart Hearing Aids

NCT05165121

Initial date: June 24, 2021

Final date: June 21, 2022

REVISED Statistical Analysis Plan

This statistical analysis plan discusses two studies: the first is a Human Factors study on the safety and usability of a subject device, the MDHearing Smart Hearing Aid; the second is a Clinical Performance study focused on examining efficacy of the subject device. Both studies recruited samples of untrained participants from the intended user population of the devices.

1. Human Factors Study

The human factors study will assess safety and usability of the subject device by providing participants with the packaged device and accompanying User Manuals and training materials. All participants will complete hands-on use scenarios and knowledge tasks with the devices in a simulated intended use environment.

1.1. Primary Endpoints

Usability will be established if the majority of participants are able to complete the use tasks, referencing the included User Manual as needed.

1.2. Secondary Endpoints

The primary safety endpoint is evaluated by tabulations of adverse events. Another aspect of safety evaluated will be participants' responses to questionnaire items about hearing health safety issues.

2. Clinical Performance Study

The clinical performance study will use a randomized, controlled field trial to examine safety and effectiveness of the subject device, comparing hearing aid outcomes for self-fitting of the device to professional-fitting of the same device.

2.1. Primary Endpoints

The primary endpoint is user-reported (subjective) aided benefit with the subject devices. This endpoint is met if the self-fit group demonstrates significantly non-inferior aided benefit to the professional-fit group as assessed with two standard questionnaires: 1) Abbreviated Profile of Hearing Aid Benefit (APHAB), and 2) 12-item short form of the Speech, Spatial, and Qualities of Hearing scale (SSQ12).

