2.3. Secondary Endpoints and Other Effectiveness Measures

The Clinical study will have the following secondary endpoints: speech-in-noise (objective) aided benefit, self-fit user satisfaction, appropriateness (or validity) and reliability of self-fitting method, and robustness of the personalization process to estimate hearing sensitivity for self-fitting using the MDHearing app.

Objective benefit will be considered acceptable if self-fit users have significantly non-inferior benefit scores for speech in noise performance on the QuickSIN compared with the professionally-fit group.

Quick SIN will be performed at two presentation levels: 70 dB HL and Most Comfortable Loudness Level (MCL).

Self-fit participants' satisfaction with sound quality, cost of devices, and ease of device use is evaluated by questionnaire. Sound quality and device cost is considered satisfactory if a majority of respondents are "satisfied" or "very satisfied" according to questionnaire responses; ease of use is considered satisfactory if a majority of questionnaire responses indicate that the hearing aids were easy to operate or that they were able to operate the devices.

The reliability and validity endpoints for in-lab hearing aid performance testing are probe-microphone measures of hearing aid output in the ear canal. The self-fitting method is considered to be reliable if average mean absolute differences (MAD) in the real ear aided response (REAR) measured from 500-4000 Hz after each experimental trial (or run) of user-based self-fitting is 5 dB or less with significance testing. The REAR of professionally-selected hearing aid settings achieved as part of the initial fitting of the hearing aids for professional-fit group participants will be evaluated for proximity to NAL-NL2 prescriptive targets at the respective test frequencies, and amplification will be deemed adequate for the intended user population (adults with mild to moderate hearing loss) if a subjectively close approximation to targets, on average, is achieved.

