Participants' hearing levels in each ear from 500-6000 Hz as measured in a quiet room using the MDHearing app installed on a smartphone or tablet (i.e., the personal profile) is compared to their "gold standard" audiometric pure tone thresholds obtained by a clinician using an audiometer in a double-walled sound-treated booth to evaluate the robustness of the personalization process for estimating hearing sensitivity using the MDHearing app; this endpoint will be met if the average difference between personal profile and audiogram is within 10 dB, with a 95% confidence interval.

3. Software

All analyses will be performed using an established statistical computing software (MATLAB, R, JMP).

4. Data Collection

Due to the COVID-19 pandemic, it is understood some subjects may not be able to attend their appointments as scheduled. In that case, subjects will be scheduled as soon as they are able to safely attend appointments. Missing data will be noted as such.

5. Data Use

Human factors endpoints will be used to determine if the current user manual and/or MDHearing app need to be adjusted to ensure user success and safe operation of the devices.

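### The primary endpoint (APHAB and SSQ12) and the QuickSIN endpoint are decided by non-inferiority, but no margin, alpha or confidence-interval rule is given

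*SAP*

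**What the plan says.** SAP 2.1 makes user-reported aided benefit the primary endpoint and gives its criterion in one sentence: "This endpoint is met if the self-fit group demonstrates significantly non-inferior aided benefit to the professional-fit group as assessed with two standard questionnaires". The questionnaires are APHAB and SSQ12. The SAP does not say which APHAB score is analysed.

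SAP 2.3 accepts objective benefit if self-fit users have "significantly non-inferior benefit scores for speech in noise performance on the QuickSIN compared with the professionally-fit group". QuickSIN is run at two presentation levels, 70 dB HL and most comfortable loudness, and the SAP does not say which level decides.

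Two other endpoints in SAP 2.3 do carry numeric limits. Self-fitting is reliable if the average mean absolute difference in real-ear response "is 5 dB or less with significance testing". For the app's hearing estimate, "this endpoint will be met if the average difference between personal profile and audiogram is within 10 dB, with a 95% confidence interval".

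The protocol (Part Three, Second visit) gives one instruction for QuickSIN and repeats it for the two questionnaires: "Compare results for statistically significant differences".

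**The concern.** Non-inferiority has meaning only relative to a margin. Without one, the word significantly in SAP 2.1 and 2.3 has no null hypothesis to refer to, and two analysts with the same data could reach opposite verdicts on the sole primary effectiveness criterion.

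The gap can be filled in two unsatisfactory ways. One is to choose a margin once the between-group difference is known. The other is to fall back on the protocol's difference test and treat a non-significant result as non-inferiority, which would reward imprecision. In either case the trial would not answer the question that it sets itself, whether self-fitting is acceptably close to professional fitting.

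**Working it through.** **1. What is specified for each endpoint**

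| Endpoint | Numeric limit | Alpha or interval |
|---|---|---|
| APHAB, SSQ12 (SAP 2.1) | none | none |
| QuickSIN (SAP 2.3) | none | none |
| Self-fit reliability (SAP 2.3) | 5 dB | significance testing, level not given |
| App profile against audiogram (SAP 2.3) | 10 dB | 95% confidence interval |

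The sentences in SAP 2.1 and 2.3 are complete, with no redaction mark or broken table beside them. The protocol's pointer to a figure in an external submission follows the gain-settings comparison, not these scores.

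**2. The plan's own figure**

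Protocol Part Three plans 75 subjects, half per group. This number cannot be reproduced, because no margin, SD, alpha, power or assumed difference is given.

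**3. Why a difference test cannot stand in**

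Let D be self-fit minus professional-fit benefit, with higher meaning more benefit, and let M be the margin. Non-inferiority requires the lower confidence bound for D to exceed −M. Non-significance requires only that the interval contains 0.

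Assume a 37/38 split, no dropout, an unadjusted two-sample comparison and units of one SD of the benefit score:

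- SE = √(1/37 + 1/38) = 0.231
- t(0.975; 73 df) = 1.993
- 95% half-width = 1.993 × 0.231 = 0.460

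An observed D of −0.40 gives an interval from −0.86 to +0.06. That is non-significant, yet compatible with a deficit of more than 0.8 SD.

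The probability of a non-significant result under a true deficit d is P(|T| < 1.993), with T noncentral t on 73 df and noncentrality d/SE in absolute value:

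- d = 0.3: 0.3/0.231 = 1.30, probability about 75%
- d = 0.5: 0.5/0.231 = 2.16, probability about 43%

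**4. How far the missing margin moves the verdict**

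The margins below are assumed, as is a true difference of 0. One questionnaire passes with probability P(T > 1.993), noncentrality M/SE. For both questionnaires, the lower figure takes their correlation as 0 and the upper as 0.8 (simulated).

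| Margin (SD) | One passes | Both pass |
|---|---|---|
| 0.4 | 0.401 | 0.16–0.30 |
| 0.5 | 0.570 | 0.33–0.47 |
| 0.75 | 0.893 | 0.80–0.85 |

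The lower figures agree with the squares: 0.401² = 0.161, 0.570² = 0.325, 0.893² = 0.797.

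Now suppose the analysis adjusts for a covariate correlated 0.5 with the benefit score (also assumed). The residual SD is √0.75 = 0.866, the SE is 0.866 × 0.231 = 0.200, and the half-width on 72 df is 0.399. Both questionnaires then pass with probability 0.26–0.40, 0.48–0.60 and 0.92–0.94 at the same margins.

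Moving the margin from 0.4 to 0.75 SD thus shifts the pass probability by more than 50 percentage points under either analysis.

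**5. Alpha matters too**

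The smallest margin giving 80% power on one questionnaire, by normal approximation, is:

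- one-sided 0.025: (1.960 + 0.842) × 0.231 = 0.65 SD
- one-sided 0.05: (1.645 + 0.842) × 0.231 = 0.57 SD

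**The case against.** **The figures are all assumed.** No SD, margin, correlation or covariate effect is in the documents, and the sample size comes from the protocol, since the SAP states none. Pass probability depends on the margin in any non-inferiority trial, so the 50-point shift reflects the margins chosen for the table. This stands. The omission does not need the figures; they only show its consequence.

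**The margin may exist elsewhere.** The SAP is headed as revised, so there was an earlier version that the reader does not have. Whether it held a margin is unknown. If a dated record fixed one, citing it answers the timing concern.

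**The SAP is later than the protocol.** Its final date is June 2022 against July 2020, and it specifies a between-group comparison, so it probably supersedes the difference test. It does not say so, and superseding that test would still leave no margin. For the questionnaires the protocol also leaves open whether the comparison is between groups or between visits, since both scales are completed at each visit. That is a side note.

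**A two-sided 95% interval is a convention.** Agreed. What is needed is a stated level and a justified margin; another pre-specified level would serve.

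**Joint success is already implied.** SAP 2.1 joins the two questionnaires with *and*, so stating that both must pass is clarification.

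A reader might also infer that the margin was, or will be, chosen with outcomes in hand, because the SAP introduction says "Both studies recruited samples of untrained participants from the intended user population of the devices". The documents do not support that: SAP 2 describes the trial in the future tense, and recruitment is not unblinding.

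**Conclusion.** The concern holds. SAP 2.1 and 2.3 make non-inferiority the success criterion for APHAB, SSQ12 and QuickSIN, and neither document supplies a margin, an alpha or a confidence-interval rule. This is more than missing detail, because the primary verdict cannot be determined from the plan as written. It should be fixed before the primary result is interpreted. The unnamed APHAB score belongs to the same gap, since a margin in points must attach to a named score. The choice of QuickSIN level is a lesser point.

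The documents give no basis for a size in scale points. The SD-unit results rest on a 37/38 split, no dropout, no true difference for the pass probabilities, and assumed margins and correlations.

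Three stronger readings are not supported:

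- **That 75 subjects are too few.** At 0.75 SD both questionnaires pass 80–94% of the time across the two analyses; at 0.4 SD, 16–40%. Without a margin, adequacy cannot be judged either way.
- **That a non-significant difference will count as success.** Neither document says so.
- **That any result must now be post hoc.** That follows only if outcomes have been seen and no earlier dated record fixed the margin.

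**What to change.** In SAP 2.1 and 2.3:

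- Name the score analysed for each instrument: the APHAB score, SSQ12 and QuickSIN, each oriented so that higher means more benefit.
- State one rule: the unfavourable bound of a pre-specified confidence interval for self-fit minus professional-fit benefit (for example two-sided 95%, equivalent to one-sided 0.025) must lie inside a margin given in scale points, with a written justification for each margin.
- State that both questionnaires must pass, and which QuickSIN level or levels decide.
- State that this rule replaces the protocol's difference test for the between-group comparison.

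Fix the margins before outcomes are opened, or cite the earlier dated record that fixed them. If neither is possible, label the non-inferiority result post hoc.

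The cost is wording in two SAP sections and a justification for each margin; recruitment and visits do not change. The real downside is that a strict justified margin may leave the result inconclusive. On the illustrative assumptions, at 0.5 SD both questionnaires pass about 33–47% of the time unadjusted and 48–60% adjusted. The rule cannot be called harder to meet than the present one, because the present text contains no operable rule for comparison.

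### The SAP does not say whether or how first-visit APHAB, SSQ-12 and QuickSIN scores enter the non-inferiority comparison; a baseline-adjusted ANCOVA would usually narrow the interval at almost no cost

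*SAP*

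**What the plan says.** Protocol Part Three, First visit, lists the two questionnaires ("Subjects complete the Abbreviated Profile of Hearing Aid Benefit (APHAB) and Speech, Spatial, and Qualities of Hearing Scale (SSQ-12") and QuickSIN ahead of tubing selection and fitting. Under Second visit, one month later, all three are repeated. For QuickSIN the instruction is "Perform Quick SIN on subjects in both groups. Compare results for statistically significant differences", and the questionnaires get the same comparison instruction.

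SAP 2.1 sets the primary criterion on the two questionnaires: "This endpoint is met if the self-fit group demonstrates significantly non-inferior aided benefit to the professional-fit group". SAP 2.3 asks QuickSIN to show "significantly non-inferior benefit scores for speech in noise performance on the QuickSIN compared with the professionally-fit group", and runs the test at two presentation levels, 70 dB HL and most comfortable loudness.

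Neither document defines benefit, names a model or covariate for these comparisons, or gives a margin. SAP section 3 names software only. The Protocol describes some balancing of the arms ("The groups are controlled for demographic such as age, gender, length of hearing loss, previous hearing aid use", and further factors), but first-visit scores on the three measures are not among the factors it lists.

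**The concern.** The data that usually narrow a between-arm interval are already collected, yet the plan does not commit to using them. With 75 subjects split in half, the interval set against any margin will be fairly wide, and in a non-inferiority test its width bears directly on whether the criterion can be met.

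The wording also fits more than one analysis: the change between visits, the second-visit score alone, or an aided-versus-unaided contrast. The first two can give different answers on the same data when the arms differ by chance at the first visit. A pass/fail rule should not leave that choice open until results are in hand.

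**Working it through.** The plan states no power or precision calculation for these measures, so there is no figure to reproduce. The check compares interval widths under three analyses.

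**Inputs.** From the documents: 75 subjects, half per arm (Protocol Part Three), taken as 38 versus 37. Assumed: a two-sided 95% interval; a common variance and slope in both arms; r, the correlation between first- and second-visit scores, of 0.3, 0.5 and 0.7; k, the second-visit SD divided by the first-visit SD, from 0.75 to 1.5. Widths are in units of the first-visit SD.

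**Half-widths**, with N = 75 and f = √(1/38 + 1/37) = 0.231:

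- Change score: t(73) × √(1 + k² − 2rk) × f
- Second visit only: t(73) × k × f
- ANCOVA, one covariate: t(72) × k√(1 − r²) × √(72/71) × f

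Here t(73) = 1.9930 and t(72) = 1.9935. For r = 0.5 and k = 1, the change score gives 1.9930 × 1 × 0.231 = 0.460. ANCOVA gives 1.9935 × 0.866 × 1.007 × 0.231 = 0.402, about 13% narrower.

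**Equal SDs (k = 1)**

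| r | Change | Second visit only | ANCOVA | Narrower than change | Narrower than second visit only |
|---|---|---|---|---|---|
| 0.3 | 0.545 | 0.460 | 0.442 | 19% | 4% |
| 0.5 | 0.460 | 0.460 | 0.402 | 13% | 13% |
| 0.7 | 0.357 | 0.460 | 0.331 | 7% | 28% |

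With 30 versus 30 completers the rounded percentages are the same. A simulation of 8,000 trials per r (38 versus 37) gave 18.8%, 12.7% and 7.1% against the change score, and 3.9%, 12.9% and 28.1% against the second-visit score.

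**Unequal SDs: ANCOVA against the change score, 38 versus 37**

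| k | r = 0.3 | r = 0.5 | r = 0.7 |
|---|---|---|---|
| 0.75 | 32% narrower | 27% narrower | 25% narrower |
| 1.25 | 11% narrower | 5% narrower | 0.2% narrower |
| 1.5 | 6% narrower | 1% narrower | 0.6% wider |

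The gain over a second-visit-only analysis does not depend on k.

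**Worst case for one covariate.** Since k²(1 − r²) ≤ k², and k²(1 − r²) ≤ 1 + k² − 2rk because (1 − rk)² ≥ 0, the average width ratio cannot exceed √(72/71) × t(72)/t(73) = 1.007. With 30 versus 30 it is 1.009.

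**Added allocation factors.** The Protocol names seven. If all seven entered as single terms beside the first-visit score, and none of the eight terms carried information or was balanced by design, the ratio would be √(72/64) × t(65)/t(73) = 1.06, or √(57/49) × t(50)/t(58) = 1.08 with 30 versus 30.

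**Same answer for two readings.** In a regression of y on arm and x, replacing y by y − x lowers the coefficient of x by one and leaves the arm coefficient and its standard error unchanged. With the first-visit score as covariate, the second-visit score and the change score therefore give the same arm estimate and interval.

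**Why the choice can matter in one trial.** The SE of the first-visit difference between arms is 0.231 SD, so a chance difference beyond 0.3 SD in either direction has probability 2 × [1 − Φ(0.3/0.231)] = 19%. At r = 0.5 and k = 1, a 0.3 SD imbalance shifts the second-visit difference by 0.5 × 0.3 = 0.15 SD one way and the change-score difference by 0.15 SD the other. ANCOVA removes that conditional shift. Over repeated randomisations all three estimates are unbiased.

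**The case against.** A reader might infer that the SAP discards the first-visit scores. The documents do not support that. A benefit score normally needs a reference condition, and the measures are listed before fitting and repeated after a month of wear. The natural joint reading is change from the first visit, which does use them. The gap is that the SAP never says so, nor whether any adjustment is made.

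A reader might also infer that the planned comparison is biased. It is not: SAP section 2 describes a randomised trial, and an unadjusted comparison is then valid.

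On the change-score reading, ANCOVA is a gain in efficiency whose size rests on a correlation and an SD ratio that the documents do not give. It runs from 32% narrower to 0.6% wider over the range examined. The largest gain at equal SDs, 28%, is against a second-visit-only analysis, the reading that fits the word benefit least. This objection stands, and it limits the claim to a likely gain with a small bounded loss.

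With no margin stated, a narrower interval cannot be translated into pass or fail. That also stands: the missing margin is a separate and more basic gap, which ANCOVA does not fill. Finally, the figures do not cover a contrast of aided and unaided scores both taken at the second visit, but neither document describes an unaided test at that visit.

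**Conclusion.** The concern holds as a precision and prespecification improvement that should be made. The unadjusted analysis the SAP most likely intends is valid, but the role of the first-visit score is unstated for the primary endpoint and for QuickSIN. At equal SDs the adjusted interval would be about 7% to 19% narrower than a change-score interval for r between 0.7 and 0.3. The gain disappears when the second-visit SD is much larger and r is high. The average loss from the single covariate is at most about 0.7% (0.9% with 30 versus 30).

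These sizes rest on assumed r and k, a common slope and variance, near-complete follow-up and random allocation. The SAP calls the trial randomised, while the Protocol says only that subjects are split into two groups and controlled for listed factors. The precision argument relies on the SAP's description.

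**What to change.** In SAP 2.1 and 2.3:

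1. Make the primary between-arm estimate for each measure an ANCOVA of the second-visit score on arm, with the same measure's first-visit score as covariate. For QuickSIN, use the matching presentation level where it was collected at the first visit; where it was not, say that the adjusted analysis is unavailable at that level.
2. Add only those balancing factors actually used in allocation.
3. Apply the non-inferiority margin, once stated for each measure, to the adjusted confidence interval.
4. Report the unadjusted change-score difference as a sensitivity analysis.
5. State the first-visit listening condition (unaided or with the subject's own aids, since previous hearing aid use is among the balancing factors) and which QuickSIN level is run at each visit.
6. Fix this before outcomes are seen by arm. The SAP introduction already speaks of recruitment in the past tense, so if outcomes have been seen, label the ANCOVA post hoc.

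The cost is SAP wording, one degree of freedom plus any for allocation factors, and a rule for subjects without a first-visit score, because SAP section 4 says only that missing data will be noted. No new measurements are needed.
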